The 344 caregivers enrolled in the RCT for a 12-month follow-up will complete an intervieweradministered baseline survey (by phone, video or online) and phone- or web-based follow-up surveys at 7 days, one month, 3 months, and 12 months after the index visit. The 50 additional male caregivers enrolled in the RCT for a 3-month follow-up will complete an interviewer-administered baseline survey (by phone, video or online) and phone- or web-based follow-up surveys at 7 days, one month, and 3 months after the index visit. Surveys will elicit self-reported data in the following domains: caregiver status, caregiver sociodemographic characteristics (e.g., age, race/ethnicity, sex and gender), caregiver-reported care recipient demographics (e.g. age, race/ethnicity), employment, household composition, income and insurance status, stage of dementia of the care recipient; psychosocial characteristics (e.g., caregiver self-efficacy, unmet health-related social and caregiving needs, burden, depression, stress and well-being); behaviors (e.g., use of resources, use of the Community Resource Finder, resource information sharing, activation of the Community Resource Specialist); health and healthcare use (e.g., physical health and healthrelated quality of life and healthcare utilization); and healthcare experience (e.g., satisfaction with care, stigma). Caregivers will be asked a limited number of questions as proxy for the care recipient to assess: well-being, community resource needs and use, health and healthcare utilization.

If needed to supplement healthcare utilization data, we will obtain health insurance claims for the participant. The informed consent/assent process will inform study participants of the rationale for accessing these data and request participants' permission to do so.

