**Analysis and Sample Size Justification** Physician concern about negatively impacting patient satisfaction or causing stigma are barriers to intervening to address unmet needs. To address these, we hypothesize that satisfaction with care will not be significantly diminished among caregivers randomized to CRx-D compared to those randomized to usual care. Aim 2 analyses will include all caregivers enrolled in the trial (N=344).

We will use the analytic approach described for Aim 1. Here, we discuss analytic issues unique to Aim 2. To facilitate ease of interpretation of the primary outcome, we will linearly rescale the composite score for the PSQ-18 subdomain of general satisfaction (questions 3 and 17). Five possible responses for each of the two items are scored 1 to 5; with a higher score equating to higher satisfaction. Scores will be transformed using the formula: y= 100 \* (x-a)/(b-a) where y=the transformed score, x=the original score, a=the minimum possible score and b=the maximum possible score. Transformed items will be averaged to generate the composite score (range 0-100). Of particular interest for the non-inferiority hypothesis (H2b) will be the confidence interval for the difference (usual care - CRx-D) and whether or not the upper limit of the confidence interval exceeds the non-inferiority margin. Of note, superiority of the intervention with respect to stigma, unmet needs and other outcomes will also be tested as this can be done without penalty. Caregiver satisfaction will be measured at 7 days following the baseline outpatient visit; no longitudinal analyses will be conducted for this outcome. Typically, analyses of patient satisfaction data adjust for case-mix (age, education and general health status); this will be feasible, but given the randomized design and single-site analysis, adjustment should not be necessary. In addition,

to determine whether there are substantial differences in the intervention's effect on ADRD caregivers with unmet HRSNs compared to ADRD caregivers without unmet HRSNs, the intervention by unmet HRSNs interaction will be tested. As in Aim 1, we will examine for differential intervention effects on primary and secondary outcomes among racial and ethnic groups, and by sex, using effect modification analyses. Some analyses will be restricted to the group without HRSNs (N=172) to provide a more complete assessment of the impact of the intervention on this group (e.g., incidence of unmet HRSNs over time).

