The proposed sample size of 344 is sufficient based on a non-inferiority margin of 7.6 points in patient satisfaction (primary outcome) assuming group allocation 1:1, power=0.8, one-sided  $\alpha$ =0.025, standard deviation=25. The non-inferiority margin of 7.6 points is less than half of the standard deviation for mean transformed general satisfaction scores in a population-based sample (e.g., male [mean=65, SD=23], female [mean=64, SD=24]); half a standard deviation is considered a minimally important difference.

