### **Experiences of Discrimination**

To assess stigma, we will use the Discrimination in Medical Settings Scale (DMS) [and it will be assessed on day 7]. The DMS was adapted from the Everyday Discrimination Scale for medical settings and has been tested for reliability and validity among African Americans and used in studies of Korean American and American Indian women. It includes 7 items, each scored on a 1 to 5 scale to generate an overall score [range 7-35, higher scores indicating more frequent discrimination].

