#### Sample Size

Aim 2 analyses will include all caregivers enrolled in the trial (N=344). The non-inferiority margin of 7.6 points is less than half of the standard deviation for mean transformed general satisfaction scores in a population-based sample (e.g., male [mean=65, SD=23], female [mean=64, SD=24]); half a standard deviation is considered a minimally important difference. [Calculations assumed power=0.8, one-sided alpha=0.025, and standard deviation=25]

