### Analysis Plan

# *Aim* 1 Analytic Plan [Aim 1 analytic plan is included here because it was referenced in Aim 2 due to overlap)

To determine the impact of CRx-D on the highest risk group, Aim 1 analyses will focus on 172 caregivers with at least 1 HRSN. Descriptive statistics will be used to summarize, overall and by study arm, sociodemographic characteristics and primary and secondary outcomes at each measured time point. The mean, standard deviation, median, and inter-quartile range will be generated for continuous variables; frequency counts and percentages will be generated for categorical variables.

The main analyses will follow the principle of intent-to-treat, and include all 172 ADRD caregivers with at least 1 unmet HRSN in the study arm to which they were allocated.

To fully leverage the longitudinal data, generalized linear mixed-effects models (GLMM) will be fit with particular interest in the time (7, 30, 90 days and 12 months post-enrollment) by study arm interaction; baseline values will be included as a covariate. Based on this model, appropriate

contrasts to test the intervention effect at specific time points (e.g., 12 months) will be constructed. These contrasts will permit examination of early versus late intervention effects, valuable information for future iterations of this and other ADRD caregiver self- and family management interventions. GLMM can be used for continuous (e.g., mean caregiver self-efficacy for providing care score, patient satisfaction score, stigma score), ordinal (e.g., physical health of PWD by proxy) or binary (e.g., resource use, resource sharing) outcomes. Models will include covariates moderately associated with the outcome to remove differences attributable to baseline covariates and increase precision of the estimate of the treatment affect. Latent growth curve modeling is a viable alternative to GLMM and will be explored when sufficient variability in the distributions of patterns of outcomes by time points exist (e.g., with the binary outcomes there will be a limited number of potential patterns).

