## Aim 2:

Since the non-inferiority margin of 7.6 for satisfaction with care is a relative effect size of 0.3 standard deviations, this relative effect size will be used as the non-inferiority margin for the secondary outcome of discrimination.

More formally, non-inferiority testing will use linear regression:  $Y = \beta 0 + \beta 1 * T + \varepsilon$ , where Y is the outcome (satisfaction with care or discrimination) and T is the treatment group indicator. The 95% CI for  $\beta 1$  will be of particular interest.

Since a majority of participants were female and African American or Black, formal interaction testing was not performed. However, a sensitivity analysis was performed that restricted analyses to females.

An additional sensitivity analysis was performed that restricted the analysis to those who selfcompleted the 1-week survey online (vs. via phone interview).

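### The two Aim 2 non-inferiority outcomes are analysed without a baseline score, which gives up precision (not validity) and leaves the SAP's wording on the baseline covariate unsettled

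*SAP*

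**What the plan says.** **Timing.** In the Overall SAP (Aim 2, Analysis and Sample Size Justification), satisfaction has one time point: "Caregiver satisfaction will be measured at 7 days following the baseline outpatient visit; no longitudinal analyses will be conducted for this outcome". The Aim 2 SAP (Measures Used, Experiences of Discrimination) adds a bracketed note on the DMS: "and it will be assessed on day 7". Neither place names a baseline score.

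**Adopted approach.** Aim 2 says it follows the Aim 1 analysis, and the Aim 2 SAP reprints that plan. The reprinted mixed-model paragraph states that "baseline values will be included as a covariate" and gives the satisfaction and stigma scores as examples of continuous outcomes.

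**Model specified.** The Aim 2 SAP (Additional Information, Clarification, Changes) states that "non-inferiority testing will use linear regression". The equation has an intercept, a treatment indicator and an error term, for satisfaction and discrimination alike. The text also judges case-mix adjustment unneeded, but the variables it means are age, schooling and overall health.

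**Survey content.** The final protocol (section C, Methodology) describes the baseline and follow-up surveys together. Among the domains they elicit it lists "healthcare experience (e.g., satisfaction with care, stigma", without tying these to a wave. The Overall SAP places the intervention arm's baseline survey before CRx-D is delivered. It refers to a Table 1 of measures and time points that is not in the text available for this review.

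**The concern.** The reprinted plan and the non-inferiority equation do not match. One carries a baseline covariate and names these two scores; the other has no such term and does not say that it replaces the first. An analyst cannot tell from the text whether a baseline PSQ-18 or DMS score exists or whether it should be used.

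The stake is precision. Both outcomes are judged by a confidence limit against a fixed margin, and the sample size sits almost exactly at 80% power with no allowance for missing day-7 data. If people who are satisfied, or who report discrimination, at baseline tend to answer alike a week later, a baseline term would remove that shared variation and narrow the interval at almost no cost.

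**Working it through.** **Inputs from the SAP.** Margin, allocation and power: "non-inferiority margin of 7.6 points in patient satisfaction (primary outcome) assuming group allocation 1:1, power=0.8". Error rate and spread: "Calculations assumed power=0.8, one-sided alpha=0.025, and standard deviation=25". Sample: "Aim 2 analyses will include all caregivers enrolled in the trial (N=344"), so 172 per arm. The discrimination margin is 0.3 SD.

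**Input not in the documents.** The correlation r between the baseline and day-7 scores. I assume 0.3 to 0.7.

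**Step 1: reproduce the plan's figure.** With no true difference,

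n per arm = 2 × 25² × (1.960 + 0.842)² / 7.6² ≈ 170, or 340 in total.

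A noncentral-t calculation needs 171 per arm (342). The stated 344 is reproduced to within rounding, from an unadjusted SD of 25. The sample size therefore does not rely on a baseline covariate.

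**Step 2: the unadjusted interval.**

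- SE = 25 × √(2/172) = 2.696
- 95% half-width = 1.96 × 2.696 = 5.28 points
- Power = Φ(7.6/2.696 − 1.96) = Φ(0.859) = 80.5%

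**Step 3: add the baseline score.** In a linear model with the baseline value, the residual SD is 25 × √(1 − r²), so the SE shrinks by the factor √(1 − r²).

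| Assumed r | Factor | 95% half-width | Power at 172 per arm | n per arm for 80% power |
|---|---|---|---|---|
| 0 (as planned) | 1.000 | 5.28 | 80.5% | 170 |
| 0.3 | 0.954 | 5.04 | 84.0% | 155 |
| 0.5 | 0.866 | 4.58 | 90.2% | 128 |
| 0.7 | 0.714 | 3.77 | 97.7% | 87 |

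The interval narrows by about 5%, 13% and 29%.

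**Step 4: discrimination.** In SD units the SE is √(2/172) = 0.1078, so power at a 0.3 SD margin is Φ(0.3/0.1078 − 1.96) = 79.4%. This is slightly below the satisfaction figure because 7.6/25 is 0.304, not 0.300. The same factors apply to its SE.

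**Step 5: loss to follow-up.** The SAP allows for 25% attrition in Aim 1 (a 12-month outcome) but nothing in Aim 2. Day-7 loss may well be smaller, so these are bounds only. Unadjusted power is 76.3% with 10% missing (about 155 per arm) and 68.5% with 25% missing (129 per arm). At r = 0.5 the residual variance is 75% of the original, which exactly offsets a 25% loss and returns power to 80.5%.

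**The case against.** The best defence is that nothing required is missing. In the Aim 1 plan the baseline covariate belongs to the longitudinal mixed model. Aim 2 rules out longitudinal analysis of satisfaction and later gives a specific, treatment-only equation. Specific text normally governs general text, randomization makes the unadjusted comparison valid, and 344 was sized without a covariate. All of that stands, and it is why the matter is one of precision. It does not settle the wording, because the equation is presented as a formalisation of the plan and the case-mix remark says nothing about a baseline value of the outcome itself.

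The gain also rests on an unstated correlation and is modest at 0.3. That stands too.

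Two stronger readings are tempting, and the documents support neither.

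- A reader might infer that the baseline covariate has no visit at which it could be collected. A pre-intervention baseline survey exists, the protocol's domain list may already place these items in it, and the table of time points cannot be seen. All that can be said is that the SAP text names no baseline score.
- A reader might infer that discrimination experienced before enrollment biases the DMS test toward non-inferiority. Randomization balances that component in expectation. It adds variance, which makes non-inferiority harder to show. If the DMS responds weakly to a one-week intervention, a baseline term would estimate the same expected difference and restore no sensitivity. The SAP text gives no DMS recall period on which to build the argument.

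**Conclusion.** The point holds as lost precision plus an unresolved wording conflict. The planned test is valid, the stated sample size reproduces, and no bias in either non-inferiority comparison is shown. For satisfaction, a baseline term would cut the 95% half-width by 0.24 points (5.28 − 5.04) at r = 0.3 and by 1.51 points (5.28 − 3.77) at r = 0.7, raising power by about 3.5 to 17 percentage points. Discrimination gains in the same proportion.

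These figures assume 172 analysed per arm, SD 25, no true difference, a linear relation between baseline and day-7 scores, and the assumed range of r. Whether the gain is available depends on whether the baseline survey holds the items, which the available text does not settle.

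**What to change.** First, state whether the two PSQ-18 general-satisfaction items and the seven DMS items are in the baseline survey. Then:

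- **If they are:** change the non-inferiority model to Y = β0 + β1·T + β2·(baseline Y) + ε for both outcomes. Keep the margins at 7.6 points and 0.3 of the unadjusted day-7 SD, and say explicitly that the residual SD does not rescale the second margin. Report the unadjusted interval as a sensitivity analysis. The cost is one model term.
- **If they are not, and enrollment is still open:** add the nine items to the baseline survey in both arms, before CRx-D is delivered, and use the same model. The cost is a slightly longer survey and possible carry-over from repeating items after 7 days. No extra visit is needed.
- **If they were never collected:** state that the treatment-only equation supersedes the Aim 1 baseline covariate for these two outcomes. The cost is one sentence.

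The SAP describes some Aim 2 analyses as already performed, so the second route may be closed. If results have been seen, label any adjusted analysis as added afterwards and keep the specified unadjusted test as primary.

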## Sample Size

Aim 1 [primary] analyses will include ADRD caregivers who screen positive for one or more unmet HRSNs (N=172). For the primary outcome (self-efficacy for providing care at 12 months) a sample of 86 caregivers/arm allows for detection of an intervention group difference of 0.43 points (sample size calculation using a group allocation of 1:1; power=0.8;  $\alpha$ =0.05, mean=2.8 and SD=1). With this sample size, power is sufficient to see at least a half a standard deviation (SD) difference in caregiver self-efficacy between intervention and control groups; half a standard deviation is considered a minimally important difference. Assuming 25% attrition, we will still be able to detect a difference equal to half an SD. Attrition in the pragmatic CRx-2 trial was 20%; this was an even lower-intensity intervention with no ongoing resource support nor touchpoints between follow-up surveys.

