## Handling of Missing Data

We aim to minimize missing data by employing interviewer-administered surveys and communicating to participants the protections of a Certificate of Confidentiality. Using these strategies, item non-response ranged from 0-3% in the CRx-2 trial. To avoid potential bias due to missing data, analyses will be conducted using multiple imputation with the chained equations method or inverse probability weighting to account for dropout and/or item non-response. In addition, characteristics of caregivers who complete each follow-up survey will be compared to caregivers who do not.

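### Aim 2's sample size of 344 leaves room for only 2 to 4 missing day-7 satisfaction scores, and the SAP states no allowance for non-response

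*SAP*

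**What the plan says.** The Overall Statistical Analysis Plan sizes Aim 2 in one sentence, which begins "The proposed sample size of 344 is sufficient based on a non-inferiority margin of 7.6 points in patient satisfaction" and continues "assuming group allocation 1:1, power=0.8, one-sided" alpha of 0.025 with a standard deviation of 25. The Sample Size section of the Aim 2 SAP repeats the inputs in a bracketed note: "Calculations assumed power=0.8, one-sided alpha=0.025, and standard deviation=25". The analysis set is everyone enrolled: "Aim 2 analyses will include all caregivers enrolled in the trial (N=344").

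The outcome is the general satisfaction subscale of the PSQ-18, rescaled to 0-100 and measured once, 7 days after the visit. The formal test, in the Aim 2 section on additional information and changes, is a linear regression on treatment arm alone.

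Two other places bear on missing scores. The Aim 2 section Handling of Missing Data plans multiple imputation or inverse probability weighting for dropout and item non-response, and reports that "item non-response ranged from 0-3% in the CRx-2 trial". For Aim 1, the Sample Size section adds a check that Aim 2 lacks: "Assuming 25% attrition, we will still be able to detect a difference equal to half an SD".

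**The concern.** Aim 2's calculation ends at the number enrolled. Nothing in the SAP says how many of the 344 are expected to have a usable day-7 score, although its own missing-data section plans for losses. If 344 is close to the number of scores required, ordinary non-response takes the power below the stated 80%.

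This is the power of a primary hypothesis, meant to answer physicians' worry that the intervention could harm satisfaction. If the upper confidence limit crossed the margin, a reader who believed the test had 80% power might take that as evidence of lost satisfaction, when part of the explanation could be a smaller effective sample.

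**Working it through.** **Inputs.** From the Overall SAP and the Aim 2 Sample Size section: margin 7.6, SD 25, one-sided alpha 0.025, power 0.80, 1:1 allocation, N = 344 (172 per arm). The true difference is not stated. I take it as 0, which fits the hypothesis ("we hypothesize that satisfaction with care will not be significantly diminished among caregivers randomized to CRx-D compared to those randomized to usual care") and reproduces the stated N.

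**Step 1: reproduce the plan's figure.** Scores needed per arm, normal approximation:

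n = 2 × [SD × (1.960 + 0.842) / margin]² = 2 × [25 × 2.802 / 7.6]² = 169.9, so 170 per arm, 340 in total.

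With the noncentral t distribution it is 171 per arm, 342 in total (power 80.04%). The plan's 344 is confirmed.

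**Step 2: power with complete data.** The standard error is 25 × √(2/172) = 2.696, and 7.6 / 2.696 = 2.819. The normal approximation gives Φ(2.819 − 1.960) = 80.5%; noncentral t gives 80.3%.

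**Step 3: slack.** 344 − 340 = 4 scores (1.2%) by the normal approximation; 344 − 342 = 2 scores (0.6%) by t.

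**Step 4: power under loss.** The documents give no day-7 response rate, so the rates below are assumptions. Per-arm n = 172 × response; margin 7.6; noncentral t.

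| Day-7 response | n per arm | SD 25 | SD 24 | SD 23 |
|---|---|---|---|---|
| 100% | 172.0 | 80.3% | 83.4% | 86.3% |
| 97% | 166.8 | 79.1% | 82.2% | 85.3% |
| 95% | 163.4 | 78.2% | 81.4% | 84.6% |
| 90% | 154.8 | 76.0% | 79.3% | 82.6% |
| 80% | 137.6 | 71.0% | 74.5% | 78.0% |

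The columns for 24 and 23 use the reference values that the SAP itself cites ("e.g., male [mean=65, SD=23], female [mean=64, SD=24"]).

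**Step 5: loss tolerated at each SD (t).** At SD 24, 80% power needs 316 scores, so (344 − 316)/344 = 8.1% may be missing. At SD 23 it needs 290, so 15.7% may be missing.

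**Step 6: the same shortfall as a margin.** At SD 25 the margin that has 80% power is 7.57 with complete data (t) and 7.99, about 8.0, at 90% response.

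**Step 7: comparison with Aim 1.** With 86 per arm and SD 1, the difference detectable at 80% power is 0.43. At 25% attrition (64.5 per arm) it is 0.497, still inside the half-SD target. Aim 1's statement survives its own allowance; Aim 2 has no equivalent statement.

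**The case against.** The case for leaving the text alone has four parts.

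*The arithmetic is right.* This stands. N = 344 follows from the stated inputs. What is missing is an allowance, which is a matter of reporting. A reader might infer that 80% power requires all 344 scores and that any non-response breaks it. That is not so: 340 to 342 scores suffice.

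*Day-7 loss may be small.* This also stands. It is tempting to apply the 25% allowance for Aim 1 or the 20% attrition of the previous trial and conclude that power is about 70%. The documents do not support that. The first figure belongs to a 12-month outcome, and the second is given without a time point. The only rate in Aim 2's own missing-data section is 0-3% item non-response, which alone would leave power at 79.1% or more. That rate does not cover caregivers who skip the survey altogether.

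*The planning SD is conservative.* This largely stands. An SD of 25 against the cited 23 and 24 is a real cushion, about 8% loss at SD 24. The SAP does not present it as an attrition allowance, though, and its power claim rests on 25.

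*Imputation will help.* Partly. A reader might say that imputation has nothing to draw on because the regression has no covariates. That confuses the analysis model with the imputation model, which can use baseline survey data. Even so, imputation and weighting mainly address bias. With one day-7 measurement and no strong predictors named, little lost precision should be expected back.

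Lower power also does not raise the risk of a false non-inferiority claim, and the confidence interval will show the precision achieved.

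**Conclusion.** The concern holds as a minor one. On the SAP's stated inputs, Aim 2 has about 1% slack for missing day-7 scores and states no non-response allowance, although it plans methods for missing data and Aim 1 carries an allowance. Up to about 5% loss costs roughly two points of power at SD 25. Around 10% loss the shortfall becomes worth stating: 76.0%, or 79.3% to 82.6% if the SD is 24 to 23.

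This rests on a true difference of zero, equal loss in both arms, an unadjusted comparison and little precision regained by imputation. The response rates are assumptions. Nothing here suggests that the trial is too small for its purpose or that the margin was miscalculated.

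**What to change.** 1. In both Aim 2 sample-size statements, give the power at a stated day-7 response rate, or at the achieved rate, since the SAP already reports some analyses in the past tense. Example: power is 80.3% with all 344 scores and 76.0% at 90% response, SD 25. Giving the margin that has 80% power, about 8.0 at 90% response, would serve equally as a description of precision; the decision margin of 7.6 should not move. The cost is a sentence, and a slightly less favourable figure.

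2. Include the HRSN stratum (0 or ≥1) in the non-inferiority regression, because randomization was stratified on it and the stated model omits it. If the primary analysis is already done, report this as a labelled sensitivity analysis. The variable is already collected. The documents do not allow the gain in precision to be estimated, so it should not be offered as making up the loss.

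3. Do not enrol more caregivers for this. The 50 men added under the later supplement also complete the 7-day survey, but they entered by an October 2022 amendment with gender-restricted eligibility, and the SAP fixes Aim 2 at 344. Adding them to the primary population now would be a change of analysis set, not of wording. If they are used at all, it should be in a labelled sensitivity analysis.
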